11.4 Analysis of Adverse Events

Treatment Emergent Adverse events (TEAEs) are defined as any AE with onset or increased severity after the first dose of study drug (RT/TMZ/Depatux-M) and no more than 49 days after the last dose of Depatux-M. All AE will be coded according to Medical Dictionary for Regulatory Activities (MedDRA) version 22.0 or higher.

Adverse Event Overview: The summary of subjects experiencing TEAEs by treatment arms will be summarized for the following adverse event categories.

- Any TEAE
- Any TEAE possibly related to Depatux-M
- Any TEAE with CTCAE grade 3 or higher
- Any Grade 3 or higher TEAE possibly related to Depatux-M
- Any TE serious AE (SAE)
- Any TEAE leading to discontinuation of Depatux-M
- Any treatment emergent CEAE
- Any treatment emergent CEAE with CTCAE grade 3 or higher
- Any treatment emergent CEAE leading to discontinuation of Depatux-M
- Deaths (within 49 days from last dose and after 49 days from last dose)

Summary of Adverse Event: Following summary of AE would be produced:

	Regardless of Any Relationship	Relationship to Depatux-M
Any AE (by PT in the descending order)	X	
Any Grade 3 or higher AE (by PT in the descending order of difference in incidence)	X	
Any AE (by SOC and PT)	X	
Any AE (by SOC, PT and Grade)	X	
Grade 3 or higher (by SOC and PT)	X	
SAE (by SOC and PT)	X	X
Leading to ABT-414 discontinuation (by SOC and PT)	X	X
Summary of CEAE (by SOC and PT)	X	
CEAE by highest grade for subjects (by SOC and PT)	X	
Leading to ABT-414 discontinuation (by SOC and PT)	X	

Listings of Adverse Event: The following listings of adverse events will be prepared.

- Listing of treatment-emergent serious adverse events.
- Listing of treatment-emergent AE that led to discontinuation of study drug.
- Listing of treatment-emergent fatal adverse events.
- Listing of Grade 3 or higher adverse events

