3.15 Corneal Epithelial Adverse Event Assessment

Corneal epithelial adverse events (CEAEs) will be monitored on a regular basis from initiation of study treatment until symptom resolution after deparatuzumab mafodotin discontinuation, as specified in [Section 2.1](#) and [Section 2.2](#), using the CEAE rating scale and recorded using the CEAE electronic case report form (eCRF; [Appendix H](#)). The CEAE rating scale is designed to describe the overall severity symptoms associated with ADC-related corneal epitheliopathy under a single CEAE grade, while capturing additional information about specific domains (ocular discomfort, photophobia, and blurred vision/visual acuity) that are commonly affected.

It is designed for routine use by the treating physician based on subject reporting without a requirement for formal eye examination, with the exception that a finding of corneal ulceration with impending perforation (CU) or corneal perforation (CP) would be diagnosed on examination by an eye care specialist. To maximize collection of CEAE assessments according to the study schedule, particularly to assess reversibility of OSEs after drug discontinuation, the CEAE assessment may be conducted by telephone and may incorporate information from caregivers.

For the current study symptoms related to the corneal epithelium will be recorded in this eCRF and should NOT be recorded as adverse events in the standard adverse event log.

CEAE Grade (Overall Severity of symptoms/findings related to corneal epithelial abnormalities):

- Only the impact of corneal epithelial abnormalities should be considered in evaluating the CEAE grade.
 - These symptoms generally include blurred vision (decreased visual acuity), photophobia, and ocular discomfort (various terms may be used to describe ocular discomfort).
- If visual ADL impairment is caused primarily by a condition unrelated to the corneal epithelium (e.g., central nervous system [CNS] lesion, retina, lens, optic nerve, etc.), this field should be recorded as "Not evaluable."
- Examples of Instrumental ADLs include preparing meals, shopping for groceries or clothes, using the telephone, managing money, etc.
- Examples of self-care ADLs include bathing, dressing and undressing, feeding self, using the toilet, taking medications, and not bedridden.

Ocular Discomfort

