4.3 Expected Adverse Events

Corneal Epithelial Adverse Events

For adverse events related to corneal epithelial abnormalities, associated signs and symptoms will be recorded and graded by the study investigator using the Corneal Epithelial Adverse Event eCRF, which was created by AbbVie, based on experience with ADC-related corneal epitheliopathy caused by depatuxizumab mafodotin, to address inadequacies of the CTCAE system for appropriately capturing symptoms, grading, and making dose modifications for ADC-related corneal epitheliopathy. Grading of corneal epithelial events is based on effects on visual ADL, as shown in Table 2 of the study protocol, and the eCRF is detailed in [Appendix H](#).

Events recorded in the Corneal Epithelial Adverse Event eCRF events will **not** be recorded in standard adverse event eCRFs, with the exception of a CEAE finding of CU/CP. A CEAE CU/CP would be considered a serious adverse event and would be reported as such as described below.

For eye disorders that are unrelated to corneal epithelial abnormalities (related to lens, retina, etc.), events will be reported as adverse event per usual practice using standard eCRFs and graded according to CTCAE criteria.

Deaths

Deaths that occur during the protocol-specified AE reporting period that are attributed by the investigator solely to progression of GBM should be recorded only on the study completion eCRF with disease progression as the reason for discontinuation and not on the AE eCRF. All other on-study deaths, regardless of relationship to study drug, must be recorded on the AE eCRF and immediately reported to the sponsor.

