4.4 Recording Data and Analyses of Safety Findings

The Investigator will monitor each subject for clinical and laboratory evidence of AEs on a routine basis throughout the study. Corneal epithelial adverse events will be assessed and recorded as described in Section 4.3. Otherwise, the Investigator will assess and record any AE in detail including the date of onset, event diagnosis (if known) or sign/symptom, severity, time course (end date, ongoing, intermittent), relationship of the adverse event to study drug, and any action(s) taken. For SAEs considered as having "no reasonable possibility" of being associated with study drug, the Investigator will provide another cause of the event. For adverse events to be considered intermittent, the events must be of similar nature and severity. AEs, whether in response to a query, observed by site personnel, or reported spontaneously by the subject will be recorded.

All adverse events will be followed to a satisfactory resolution, or to improvement to Grade 1 unless the subject has died before this could be determined.

With the exception of the corneal epithelial adverse events as described in Section 4.3, the National Cancer Institute Common Terminology Criteria for Adverse Events (NCI CTCAE) v.4 will be used for AE reporting/grading of event severity.

Adverse events will be coded using the Medical Dictionary for Regulatory Activities (MedDRA). The number and percentage of subjects with treatment-emergent adverse events (i.e., any event that begins

or worsens in severity after initiation of study drug through 49 days post-study drug dosing) will be tabulated by primary MedDRA System Organ Class (SOC) and preferred term. The tabulation of the number of subjects with treatment-emergent adverse events by severity grade and relationship to study drug also will be provided. Subjects reporting more than 1 adverse event for a given MedDRA preferred term will be counted only once for that term using the most severe grade according to the severity grade table and the most related according to the relationship to study drug tables. Subjects reporting more than 1 type of event within an SOC will be counted only once for that SOC.

The number and percentage of subjects with adverse events in the MedDRA Eye Disorders SOC (e.g., infection, increased intraocular pressure, cataract, etc.) will be compared between prophylactic arms across PT and SOC using Fisher's exact test.

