APPENDIX H. CORNEAL EPITHELIAL ADVERSE EVENT ECRF

CEAE Grade (Overall Severity of Symptoms/Findings Related to Corneal Epithelial Abnormalities):

NE – Not evaluable (Severity of Visual ADL impairment is determined primarily by visual problems unrelated to cornea [lens, retina, optic nerve, CNS lesion, etc.]

0 – Asymptomatic

1 – Symptomatic, but no effect on visual ADLs

2 – Instrumental ADLs* affected, but can perform instrumental ADLs independently

3 – Instrumental ADLs require assistance

4 – Self-care ADLs** require assistance

5 – Corneal perforation or corneal ulceration with impending perforation

*Instrumental ADL refer to preparing meals, shopping for groceries or clothes, using the telephone, managing money, etc.

**Self-care ADL refer to bathing, dressing and undressing, feeding self, using the toilet, taking medications, and not bedridden.

Ocular Discomfort (Including Eye Pain, Dry Eye, Foreign Body Sensation, etc.)

Symptoms: *Record all symptoms contributing to ocular discomfort (check those that apply):*

dry eye

eye pain

foreign body sensation

itching

other (specify) _____

other (specify) _____

other (specify) _____

Impact of ocular discomfort on visual ADLs:

0 – Asymptomatic

1 – Symptomatic, but no effect on visual ADLs

2 – Instrumental ADLs affected, but can perform instrumental ADLs independently

3 – Instrumental ADLs require assistance

4 – Self-care ADLs require assistance

Reading (Due to Blurred Vision)

N/A – Not Applicable (subject does not read for reasons unrelated to blurred vision)

1 – No difficulties reading

2 – Reading requires large fonts or magnification

3 – Unable to read due to blurred vision

Photophobia

0 – None

1 – Mild (bright light)

2 – Moderate (ambient light)

3 – Severe (constant)

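### SAP 11.4 tabulates related events and corneal events leading to discontinuation without saying where those data come from; if the Operations Manual is followed, these rows can hold almost no corneal events

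*SAP*

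**What the plan says.** SAP 11.4 lists the rows of the adverse event overview. Among them are "Any TEAE possibly related to Depatux-M", "Any Grade 3 or higher TEAE possibly related to Depatux-M", a row for any treatment-emergent event that led to stopping the drug, and "Any treatment emergent CEAE leading to discontinuation of Depatux-M". Two further CEAE rows count any treatment-emergent CEAE and "Any treatment emergent CEAE with CTCAE grade 3 or higher". The same section plans CEAE tables by system organ class and preferred term. It names no source dataset for CEAEs.

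The Operations Manual sends these events down a separate route. Section 3.15 says that corneal symptoms "should NOT be recorded as adverse events in the standard adverse event log". Section 4.3 says that events on the CEAE form will not "be recorded in standard adverse event eCRFs, with the exception of a CEAE finding of CU/CP" (corneal ulceration with impending perforation, or corneal perforation). Section 4.4 then divides the recording duties: "Corneal epithelial adverse events will be assessed and recorded as described in Section 4.3. Otherwise, the Investigator will assess and record any AE in detail". The detail that follows includes onset date, relationship to study drug and action taken.

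Appendix H of the Operations Manual prints the CEAE form. It begins with "CEAE Grade (Overall Severity of Symptoms/Findings Related to Corneal Epithelial Abnormalities" and continues with discomfort symptoms and their impact, reading, and photophobia. It prints no field for relationship or action taken.

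**The concern.** Ocular toxicity is the dose-limiting toxicity of this drug and the reason for the trial. A related-event row or a discontinuation row is read as a count of what happened. If corneal events cannot reach it because of how they were recorded, a low number or a zero reflects data capture rather than tolerability, and the table does not tell the reader so. All three arms would be affected, and so would anyone who sets these rows beside those of another study of the drug.

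**Working it through.** The plan gives no figure to reproduce here. The check is to trace each overview row to a form that could supply it.

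**If the Operations Manual (3.15, 4.3, 4.4) is followed**

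| Overview row | Needed for a corneal event | Standard AE record | CEAE form as printed |
|---|---|---|---|
| Any CEAE | occurrence | CU/CP only | yes |
| Grade 3+ CEAE | grade | CU/CP only | yes, on the CEAE scale rather than CTCAE |
| Any TEAE; Grade 3+ TEAE | occurrence, grade | CU/CP only | yes, but only if the form is merged in; the SAP is silent |
| Related TEAE; Grade 3+ related TEAE | causality | CU/CP only | no field printed |
| TEAE leading to discontinuation; CEAE leading to discontinuation | action taken | CU/CP only | no field printed |

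The treatment-emergent rule also needs dates. I assume that visit dates are held with the form, although Appendix H prints none.

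**Text that points the other way**

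- Protocol 6.1 has corneal events reported under a single AE term, corneal epitheliopathy. Its causality definitions carry no exemption for them.
- Operations Manual 4.2 asks for onset, relationship and action taken for any AE, also without exemption.
- SAP 11.2 identifies CEAEs by a query code (CMQ 80000184) and uses a CEAE start date. SAP 11.4 tabulates them by preferred term. All of this needs coded, dated records.

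The two routes are incompatible. If the programmer takes CEAEs from coded AE records while sites followed 3.15 and 4.3, even the two CEAE rows that the form could fill would be nearly empty. Protocol Appendix E adds a further break: its reduced schedule keeps AE assessment but lists no CEAE assessment, so corneal events after that amendment may arrive by a different route from earlier ones.

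**Illustrative size**

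Inputs: 40 enrolled (SAP 4.0) and the INTELLANCE-1 active-arm rates in Protocol 2.2. I read the 11.8% there as discontinuation for corneal events.

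- Any corneal event: 40 × 0.947 = 37.9, about 38.
- Grade 3+ corneal event: 40 × 0.610 = 24.4, about 24.
- Discontinuation: 40 × 0.118 = 4.7, about 5. The chance of at least one is 1 − (1 − 0.118)^40 = 0.99.
- Grade 3+ TEAE row built from the AE record alone: at one extreme no subject with a Grade 3+ corneal event had another Grade 3+ event, which gives 87.3% − 61.0% = 26.3%, or 10.5 of 40. At the other extreme all of them did, which gives 87.3%, or 34.9 of 40. The documents do not give the overlap.

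**The case against.** A reader might infer that the dose-limiting toxicity disappears from the safety overview. The documents do not support that. Two overview rows count any CEAE and Grade 3+ CEAE and need neither causality nor action taken. SAP 11.2 also reports Grade 3+ CEAEs within the primary endpoint and analyses time to first CEAE. On the illustrative rates, the 38 and 24 subjects would appear a few lines below the rows that miss them, provided the form is used as the source.

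A reader might also take it as established that the CEAE discontinuation row can hold only CU/CP. That is too firm. Protocol 6.1 and Operations Manual 4.2 could have led sites to complete an AE record. Appendix H prints no subject number or date, whereas the ophthalmology form in Appendix C does, so it may show only the rating content. The full CRF is not available. SAP 9.1 separately summarises reasons for stopping study drug by arm, though without listing the categories.

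Finally, it is tempting to size the loss by the INTELLANCE-1 gap in Grade 3+ events, 87.3% − 62.3% = 25.0 points. That is drug against placebo. Here every arm receives the drug, and the Protocol names non-corneal contributors to the excess (thrombocytopenia, GGT and ALT). The SAP plans no comparison with other studies, so a false reading as a safety benefit is a risk rather than a planned result.

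These points narrow the concern. They do not supply the missing rule: the documents describe two routes and SAP 11.4 adopts neither.

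**Conclusion.** The concern holds in a limited form. If the Operations Manual is followed, the rows for related TEAEs, Grade 3+ related TEAEs, TEAEs leading to discontinuation and CEAEs leading to discontinuation can hold almost no corneal events. The general TEAE and Grade 3+ TEAE rows are understated too if they are built from the AE record alone. The any-CEAE and Grade 3+ CEAE rows remain fillable from form grades.

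This rests on Appendix H showing all the fields collected, and on sites having followed sections 3.15 and 4.3. The counts of about 38, 24 and 5 of 40 are illustrative only: they come from another trial, its grading may differ from the CEAE scale, the safety population may be smaller than 40, and most subjects here lacked long follow-up.

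**What to change.** Amend SAP 11.4 before database lock:

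1. Reconcile Protocol 6.1 and Operations Manual 4.2 with Operations Manual 3.15 and 4.3. Name the CEAE source as the CEAE form, graded on the CEAE scale, plus any corneal records in the AE log.
2. Define each overview row as AE log plus CEAE form, and show it with and without CEAEs.
3. Use investigator causality where it was recorded. Otherwise footnote CEAE relatedness as not collected. A count that treats all CEAEs as related should be at most a labelled sensitivity display, because 36.1% of INTELLANCE-1 placebo subjects had corneal events (40 × 0.361 = 14.4, about 14 of 40).
4. Derive CEAE-related discontinuation from the study-drug discontinuation reason (SAP 9.1) together with the last CEAE grade before stopping, if the reason categories allow it. Otherwise report it as not collected, not as zero.

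The cost is SAP wording and modest programming, with no new data collection. Some attribution will remain uncertain.

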11.5 Analysis of Laboratory and Vital Signs Data

NCI CTCAE grading criteria for laboratory abnormalities are shown in [Table 2](#) and [Table 3](#). Pre-defined criteria for potentially clinically significant vital signs values are given in [Table 4](#).

Subjects with maximum treatment-emergent laboratory values meeting the potentially clinically significant criteria will be summarized. Similarly, subjects with treatment emergent post baseline values meeting criteria for potentially clinically significant Vital Signs values will be provided.

Table 2. Criteria for NCI CTCAE Grades for Laboratory Values - Hematology

	Units	NCI CTCAE Grade ≥ 3		NCI CTCAE Grade ≥ 4	
		Low	High	Low	High
Hematology Variables					
Hemoglobin	g/L	< 80			
White blood cell count	$10^9/L$	< 2		< 1	
Neutrophil count	$10^9/L$	< 1		< 0.5	
Lymphocyte count	$10^9/L$	< 0.5		< 0.2	
Absolute Platelet count	$10^9/L$	< 50		< 25	
Coagulation Variables					
INR increased	ratio		> 2.5 \times ULN		

Table 3. Criteria for NCI CTCAE Grades for Laboratory Values - Chemistry

Chemistry Variables	Units	NCI CTCAE Grade ≥ 3		NCI CTCAE Grade ≥ 4	
		Low	High	Low	High
Creatinine	mcmol/L		> 3 \times ULN		> 6 \times ULN
Total bilirubin	mcmol/L		> 3 \times ULN		> 10 \times ULN
ALT	U/L		> 5 \times ULN		> 20 \times ULN
AST	U/L		> 5 \times ULN		> 20 \times ULN
ALP	U/L		> 5 \times ULN		> 20 \times ULN
GGT			> 5 \times ULN		> 20 \times ULN
Sodium	mmol/L	< 130	> 155	< 120	> 160
Potassium	mmol/L	< 3	> 6	< 2.5	> 7
Calcium	mmol/L	< 1.75	> 3.1	< 1.5	> 3.4
Magnesium	mmol/L	< 0.4	> 1.23	< 0.3	> 3.3

Table 4. Criteria for Potentially Clinically Significant Vital Signs Values

Vital Signs Variables	Criterion	Definition of Potentially Clinically Significant Values
Systolic blood pressure	High	Value \geq 160 mmHg
Diastolic blood pressure	High	Value \geq 100 mmHg
Heart rate	Low	Value \leq 50 bpm
	High	Value \geq 120 bpm
Temperature	Low	Value \leq 32°C
	High	Value $>$ 40°C

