5.4 Prior and Concomitant Therapy

Continuous TMZ therapy induces lymphocytopenia and thrombocytopenia. Subjects are at an increased risk for opportunistic infections and bleeding – please consult package insert.⁶

All supportive therapy for optimal medical care will be given during the study period at the discretion of the treating Investigator. The locally approved product label, institutional guidelines, local practice, or applicable Summary of Product Characteristics (SmPC) should be referenced for any concomitant therapy guidelines.

Any medication or vaccine (including over the counter or prescription medicines, vitamins and/or herbal supplements) that the subject is receiving at the time of enrollment or receives during the study must be recorded until completion of study.

Any questions regarding concomitant or prior therapy should be raised to the AbbVie Therapeutic Area Medical Director. Information regarding potential drug interactions with depatuxizumab mafodotin can be located in the depatuxizumab mafodotin Investigator's Brochure.⁷

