7.2 Dealing with Multiple Values on the Same Day

In cases multiple values are collected on the same day at baseline or post-baseline visit the worst value will be used for further analyses.

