11.0 Safety Analysis

11.1 General Considerations

Safety analyses will be carried out on Safety population. Categorical safety endpoints (e.g., incidence of AEs, incidence of potentially clinically significant laboratory values) will be summarized using frequencies and percentages.

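### SAP 11.5 summarises laboratory values by each subject's maximum, which is the wrong direction for every Low limit, so the laboratory table would understate low-side abnormalities

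*SAP*

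**What the plan says.** SAP 11.5 introduces its criteria with "NCI CTCAE grading criteria for laboratory abnormalities are shown in" Tables 2 and 3, then gives the rule for using them: "Subjects with maximum treatment-emergent laboratory values meeting the potentially clinically significant criteria will be summarized".

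- **Table 2**, titled "Criteria for NCI CTCAE Grades for Laboratory Values - Hematology", gives Low limits only for haemoglobin, white cells, neutrophils, lymphocytes and platelets. INR, listed under coagulation, has a High limit.
- **Table 3**, titled "Criteria for NCI CTCAE Grades for Laboratory Values - Chemistry", gives High limits only for creatinine, bilirubin, ALT, AST, ALP and GGT. Sodium, potassium, calcium and magnesium have both Low and High limits.

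The next sentence of 11.5 covers vital signs and does not mention a maximum: "subjects with treatment emergent post baseline values meeting criteria for potentially clinically significant Vital Signs values will be provided". SAP 11.1 says only that "incidence of potentially clinically significant laboratory values) will be summarized using frequencies and percentages", with no direction. The SAP's one worst-value convention, in 7.2, is for values "collected on the same day at baseline or post-baseline visit the worst value will be used for further analyses". It works within a day, not across visits.

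**The concern.** The maximum of a set of values lies below a Low limit only if every value in the set does. A transient fall, which is the usual form of a treatment-related cytopenia, therefore does not meet the criterion as written.

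The affected variables matter in this trial. Protocol 5.4 states that "Continuous TMZ therapy induces lymphocytopenia and thrombocytopenia". Protocol 6.3 lists thrombocytopenia among the potential toxicities of depatuxizumab mafodotin. The INTELLANCE-1 summary in Protocol 2.2 names it among the events more frequent with the drug, including at Grade 3 or higher. The SAP describes itself as a guide to statistical programming, so a programmer who follows the sentence would produce the wrong low-side counts.

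**Working it through.** The plan states no figure on this point, so there is nothing to reproduce. The check is a count of the limits, a logical test of the rule under each plausible reading, and an illustration on assumed data.

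**1. Count of limits (SAP Tables 2 and 3)**

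| Group | Low limits | High limits |
|---|---|---|
| Haemoglobin | 1 | 0 |
| White cells, neutrophils, lymphocytes, platelets (2 each) | 8 | 0 |
| INR | 0 | 1 |
| Creatinine, bilirubin, ALT, AST, ALP, GGT (2 each) | 0 | 12 |
| Sodium, potassium, calcium, magnesium (2 Low and 2 High each) | 8 | 8 |
| Total | 17 | 21 |

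The two tables hold 16 variables and 17 + 21 = 38 limits. The maximum is right for the 21 High limits and wrong for the 17 Low ones. Five variables are affected entirely and four on their low side only.

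**2. The rule under each reading**

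Take assumed on-treatment platelet counts of 210, 160, 90, 22, 70 and 140 (10^9/L). The Table 2 limits are below 50 for Grade 3 or higher and below 25 for Grade 4 or higher.

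- *Every on-treatment value counts.* The maximum is 210, which is not below 50, so the subject is not flagged. The minimum is 22, which meets both limits.
- *Only newly low values count*, using the definition in SAP 7.3 (newly occurring or worsening). Taking below 100 as low for illustration, the values are 90, 22 and 70. The maximum is 90, so the subject is still not flagged.
- *Only values already below the Grade 3 limit count.* A subject with 45 and 22 has a maximum of 45. That meets the Grade 3 limit but not the Grade 4 limit, so a Grade 4 nadir is shown as Grade 3.
- *Maximum CTCAE grade.* This gives the right answer, but the sentence refers to values, not grades.

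**3. What the protocol implies about recovery**

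Eligibility (Protocol 5.1) requires platelets of at least 100,000/mm³, which is 100 × 10^9/L, and neutrophils of at least 1,500/mm³, which is 1.5 × 10^9/L. Both lie above the Grade 3 limits of 50 and 1. For continuing subjects, a footnote to the Appendix E schedule asks for weekly counts after a fall below those same levels, until they are regained before TMZ dosing. A subject who recovers in this way has a later platelet value of about 100 or more. On the literal reading the depth of the nadir then makes no difference.

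**4. Illustration only: every input below is assumed**

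Let q be the chance that a value is below the limit at one visit, with K independent visits. The maximum rule flags q^K and the minimum rule flags 1 − (1 − q)^K.

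- With q = 0.10 and K = 8, the maximum rule gives 0.10^8 = 1e-8 and the minimum rule gives 1 − 0.90^8 = 0.57.
- Over q from 0.05 to 0.5 and K from 4 to 12, the maximum rule flags between 2e-16 and 0.0625, and the minimum rule between 0.185 and more than 0.999.
- With correlated lognormal platelets (median 150, log-SD 0.5, 8 visits), the results by within-subject correlation are:

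| Correlation | Minimum rule flags | Maximum rule flags |
|---|---|---|
| 0.3 | 9.1% | 0.0% |
| 0.6 | 6.8% | 0.02% |
| 0.9 | 3.6% | 0.3% |

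The direction holds throughout. The size depends entirely on the assumptions.

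**The case against.** **The intent is obvious.** The tables are headed by CTCAE grade with separate Low and High columns, SAP 11.4 speaks of highest grade, and comparing a maximum with a Low column is an odd thing to program. The authors probably meant the worst value or worst grade, but the SAP does not say so. SAP 7.2 shows that it can say worst value when it means that. The treatment-emergent qualifier does not repair the rule either: the second and third readings above both still fail.

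**The AE tables cover serious cases.** A reader might infer that the trial would miss cytopenias altogether. The documents do not support that:

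- Operations Manual 3.10 requires a laboratory value that leads to interruption or discontinuation of a study treatment, or to medical intervention, to be recorded as an AE.
- Operations Manual 4.2 adds abnormalities that meet protocol criteria or that the investigator considers to be AEs.
- Table 4 in Protocol 6.3 attaches interruption of study drug to Grade 3 and Grade 4 toxicities.
- SAP 11.4 tabulates AEs by grade, tabulates Grade 3 or higher separately, and lists them.

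A Grade 4 platelet count would ordinarily reach those outputs. This part of the objection stands and limits the consequence. It does not restore the laboratory table, whose use is that it does not depend on AE reporting. A Grade 3 lymphocyte value that prompted no action could be absent from both.

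**Two further overstatements.** A reader might call the rule wrong for nine analytes outright. For the four electrolytes only the low side is affected. A reader might also expect the table to show almost no cytopenias. That rests on assumed distributions, not on anything in the documents.

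**The setting is modest.** This is an abbreviated SAP for a study stopped at 40 enrolled subjects. The arms differ only in eye prophylaxis, and laboratory profiles are listed under other safety endpoints. All of that is true, and it makes this a small correction rather than a threat to the trial's conclusions.

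**Conclusion.** The sentence is wrong as written for all five haematology variables and for the low side of sodium, potassium, calcium and magnesium. It is right for every High limit. On the literal reading, a subject who falls below a Low limit and recovers is not flagged. On the narrowest value-based reading, the grade can be understated. Nothing else in the SAP corrects this.

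The laboratory table would therefore understate low-side abnormalities, mainly those not reported as AEs. The extent cannot be derived from the documents, because they give no distribution of counts, no rate of recovery and no share of abnormalities recorded as AEs. The error itself rests on no assumption beyond taking the sentence at its word. The primary and secondary endpoints do not use this table.

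**What to change.** Replace the laboratory sentence in SAP 11.5 with:

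> Subjects whose worst treatment-emergent value in the direction of the criterion (minimum for Low limits, maximum for High limits) meets Grade ≥ 3, and Grade ≥ 4, in Tables 2 and 3 will be summarized by arm and overall.

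The two-sided electrolytes then need separate Low and High rows, which the column layout of Table 3 already allows. Presentation by arm and overall follows SAP 4.0. The cost is one sentence and the matching line of programming. No new data are needed, and no other analysis changes.
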